# 9. PROTOCOL PROCEDURES

## 9.1. Practice Identification

Practices using (or planning to use) the Hypertension Plus system for their patients will be invited to participate in the service evaluation.

Practices that are eligible to take part in the service evaluation will be provided with a welcome pack which includes:

- Practice Information Leaflet
- Copy of the protocol
- Copy of regulatory approval documentation (if required)
- Instructions on how to complete the service evaluation activities

Site agreements will be in place with each practice and as part of the contracting process will include agreement from the practices, as Data Controllers, to provide the study team with anonymised data from the clinical records and the tele-monitoring system.

# 9.2. Screening and Eligibility Assessment

TM101-A

Protocol Template for a Research Study\_version 15.0CONFIDENTIAL© Copyright: The University of Oxford and Oxford University Hospitals NHS Foundation Trust 2019Page 14 of28

Not applicable

## 9.3. Informed Consent

No direct or active involvement will be required from consulting patients and we will not be seeking individual patient consent. Anonymised outcome data will be extracted from the EHR by automatic searches and from the Hypertension Plus system and provided in an anonymised form to the analysis team. This will apply to records of patients who have not opted out of use of their health records in research

Hypertension Plus is a commercial system which has passed separate regulatory approvals including GDPR and this evaluation is of the practice utilisation of the dashboard. Patients who use the system will do this via sign up outside of the service evaluation. We will seek permission of the Data Controller for access to anonymised data concerning utilisation of the system.

## 9.4. Randomisation

This is a service evaluation that does not include randomisation. Patients in participating practices will choose to use the Hypertension Plus system in conjunction with their health care professionals.

## 9.5. Description of study intervention and comparator

## 9.5.1. Description of study intervention

The study intervention is "Hypertension Plus". People using the system will use an app to send blood pressure readings securely to a central dashboard. Data will be recorded automatically in the clinical record via appropriate SNOMED codes allowing identification of active users. An active user will be someone with a record of having used the Hypertension Plus system in their clinical record with the appropriate SNOMED code. This definition will be regardless of how much use is made of the system and once labelled as having received the intervention, patients will be analysed in that group on an "intention to treat basis".

## 9.5.2. Description of comparator

Usual care – patients on hypertension registers not using Hypertension Plus for submitting home blood pressure readings ie those without a record of having used the system as defined by clinical (SNOMED) codes.

## 9.6. Data Extraction

Routinely collected retrospective data from people with a clinical code for hypertension registered in practices taking part in the Hypertension Plus implementation will be extracted at baseline and again at 6 and 12 months. This data will include:

- Age (years)
- Gender
- Ethnicity (White, Black, Asian, Mixed, Other)
- Smoking status (current, ex or non)

#### TM101-A

Protocol Template for a Research Study\_version 15.0CONFIDENTIAL© Copyright: The University of Oxford and Oxford University Hospitals NHS Foundation Trust 2019Page 15 of28

- Index of Multiple Deprivation
- Body mass index (kg/m^2)
- Total cholesterol (mmol/L)
- Systolic and diastolic blood pressure (clinic or home readings)
- Ambulatory blood pressure
- SNOMED codes for home blood pressure measurement (in order to identify system users)
- Past medical history:
  - Diagnosis of diabetes (Type 1 or 2)
  - Previous myocardial infarction or stroke
  - Diagnosis of chronic kidney disease
  - o Estimated glomerular filtration rate (eGFR, ml/min/1.73 m^2)
- Medication use
  - Statin treatment (drug type and dose)
  - o Antihypertensive medication use (drug type and dose, defined daily dose)
  - o Other current cardiovascular medication
- Electronic Frailty Index and/or characteristics making up the electronic frailty index 
- Health Economic Resource use including consultation rate, timing, personnel undertaking, referrals and admissions.

#### 9.7. Sample Handling

Not applicable.

## 9.8. Early Discontinuation/Withdrawal of Participants

Not applicable.

## 9.9. Definition of End of Study

The end of study is the point at which all the study data has been received; i.e. the last data extraction has taken place and no further data queries are required.

#### **10. SAFETY REPORTING**

This service evaluation involves only analysis of anonymised retrospective data, so we do not anticipate any adverse effects.

## **11. STATISTICS AND ANALYSIS**

#### 11.1. Statistical Analysis Plan (SAP)

The plans for the statistical analysis of the study are outlined below. Prior to data lock and the final analysis, consideration will be made as to whether any further detail in a formal statistical analysis plan is required and if so then a SAP will be agreed before the analysis.

TM101-A

## 11.2. Description of the Statistical Methods

#### **Exposures**

The primary exposure will be use of the Hypertension Plus monitoring system, defined by SNOMED codes recorded in the clinical system compared to no use. The date on which the patients started using the system ("Time 0") will be extracted and patients will be classified as exposed from this date onwards. These patients will be classified as unexposed prior to this date. Where a practice or individual stops using the system, this will be classed as the end of exposure. Patients who never use the system will form the unexposed group.

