# 8.3. Study Patient Records

TM101-A

Protocol Template for a Research Study\_version 15.0 CONFIDENTIAL
© Copyright: The University of Oxford and Oxford University Hospitals NHS Foundation Trust 2019 Page 13 of
28

Outcome data for adult patients (>18 y) and on the hypertension register will be extracted from the EHR at each participating practice by electronic search and provided in an anonymised form to the analysis team.

Active users of the intervention will be defined as:

- Adults aged 18 years or above.
- Diagnosed with hypertension on practice hypertension registers whose baseline blood pressure is above 140/90mmHg on last recorded reading at baseline
- Registered users of the Hypertension Plus telemonitoring system with coded data in the clinical record identifying them as such

These will be compared to patients not using the system who are:

- Adults aged 18 years or above
- Diagnosed with hypertension on practice hypertension registers whose baseline blood pressure is above 140/90mmHg on last recorded reading at baseline
- With no record of using the Hypertension Plus telemonitoring system coded in the clinical record.

An exploratory analysis will examine people in the two groups above who have a blood pressure  $\leq$ 140/90mmHg at baseline, with the same comparison between users and non users of the system.

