#### Timeframe of outcome measurement

"Time 0" for exposed patients will be the date on which they start using the Hypertension Plus monitoring system. For unexposed patients "Time 0" will be the median date on which exposed patients in the same general practice started using the Hypertension Plus system. Longitudinal data for all TM101-A

Protocol Template for a Research Study\_version 15.0CONFIDENTIAL© Copyright: The University of Oxford and Oxford University Hospitals NHS Foundation Trust 2019Page 17 of28

outcomes (BP measurements, consultation dates etc.) will be extracted from patient's electronic health record from the 12 months before and after "Time 0" for all patients.

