## Statistical modelling

Multilevel models and Difference-in-Differences (DiD) analysis will be used to describe changes in outcomes over time (12 months before and after "Time 0") and the effect of the introduction of the Hypertension Plus system. Difference-in-differences (DiD) allows comparison of differences in outcomes, TM101-A

Protocol Template for a Research Study\_version 15.0 CONFIDENTIAL
© Copyright: The University of Oxford and Oxford University Hospitals NHS Foundation Trust 2019 Page 18 of
28

before and after an intervention, between groups. Bias from unobserved fixed variables within each group is automatically accounted for in this type of analysis but bias from variables that affect allocation to the exposed an unexposed group must still be accounted for.

• Primary outcome (SBP) and secondary DBP outcome:

For the primary outcome (SBP) and secondary outcome of DBP, multilevel linear models will be used to model these outcomes over time, including a fixed linear effect for time relative to "Time 0" and random effects for patient and practice level average BP. The models will also include as fixed effects, an indicator for whether each BP was measured in the clinic or at home, an indicator for exposure and, to estimate difference-in-differences, interaction terms between the exposure and time period variable (initial model).

The addition of random effects for patient and practice level trends into the initial model will be considered by comparing models via the likelihood ratio test and Akaike Information Criterion (AIC), with terms retained if model fit is significant improved or the AIC is lower. Covariates will be included as fixed effects without selection once the initial model is finalised. To account for autocorrelation between BP measurements in the same individual, standard errors will be estimated using robust methods and more specifically the Huber-White Sandwich estimator of the variance which can adjust for within-cluster correlation.

The effect of the Hypertension Plus intervention at 6 and 12 months will be estimated by comparing the estimated BP values in the exposed at unexposed groups at these time points, as derived from the models. These estimates, and estimates from the models will be summarised in tables including p-values and 95% confidence intervals.

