# TM101-A

Protocol Template for a Research Study\_version 15.0

© Copyright: The University of Oxford and Oxford University Hospitals NHS Foundation Trust 2019 Page 21 of 28

		intervention/control in the analysis b) BP control rather than BP level in analyses
(3) High variability in the frequency of readings	Home readings can be several times per day or week whereas clinic readings tending to be 1-4x per year. Furthermore, attendance at clinic may be for some other reason meaning those who attend or not are different systematically	
 
a) Primary analysis utilises all available data
 
b) Consider sensitivity analysis using standardisation of readings over time. This means that we take bp values at fixed time points more specifically at 6 and 12 months with value closest to that time point being the one used for the analysis.
 

(4) Contamination of readings	Home readings can be coded as clinic readings. The automated importing of Hypertension Plus readings into the clinical record should avoid this but it is possible that home readings in the comparator group may also be contaminated as may be readings prior to the implementation period.	
 
a) This may be a problem in both groups
 
b) Hypertension Plus readings will be labelled as such
 

(5) Regression to the mean	People chosen on the basis of raised baseline readings are more likely to have subsequently controlled BP	Both intervention and comparison groups will be chosen using same attributes Consideration of need for matching.
(6) Measurement error	Both operator, system and monitor errors are possible	Operator errors may be more likely by patients but evidence of operator bias is more likely for clinicians. Most of these errors will be similar in both groups
(7) End digit preference	People tend to be more likely to record readings ending in zero	
 
a. We will investigate prevalence in both intervention and comparator groups
 
b. Adjusting for the control/intervention group in a mixed model should be
 

		able to take into account for potential differences in the magnitude of digit preference
(8) Withdrawal bias	Patients may not use the Hypertension Plus system consistently.	We will use intention to treat approach so individuals with any Hypertension Plus activity recorded will be assigned to intervention.

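### Users count as exposed from the Time 0 date itself, so their first transmitted reading, which the system cannot yet have affected, is normally analysed as an after-period outcome in users only

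*Protocol*

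**What the plan says.** Section 11.2 (Exposures) extracts the date on which a patient began using Hypertension Plus, calls it Time 0, and states that it "will be extracted and patients will be classified as exposed from this date onwards". For the time before, it says: "These patients will be classified as unexposed prior to this date". The Time 0 day therefore belongs to the after period.

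Three places bear on what marks a user:
- Section 9.5.1: "Data will be recorded automatically in the clinical record via appropriate SNOMED codes allowing identification of active users".
- Section 9.6 lists among the items to extract "SNOMED codes for home blood pressure measurement (in order to identify system users".
- Section 8.3 uses registration wording: "Registered users of the Hypertension Plus telemonitoring system with coded data in the clinical record identifying them as such".

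For comparators, section 11.2 (Timeframe of outcome measurement) sets a Time 0 that "will be the median date on which exposed patients in the same general practice started using the Hypertension Plus system".

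The effect is carried by "interaction terms between the exposure and time period variable (initial model" (section 11.2, Statistical modelling), in a model with linear time and a home/clinic indicator. Estimates are reported at 6 and 12 months. On which readings enter, section 12.3 (row on frequency of readings) says: "Primary analysis utilises all available data". The protocol states no lag, run-in or rule for the reading that sets Time 0.

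**The concern.** Hypertension Plus acts through readings that are sent in, reviewed and followed by messages or treatment changes. None of this can precede the first reading sent, which is a starting value by nature. The rule in section 11.2 nevertheless makes it an outcome under exposure.

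The error is one-sided. A user's Time 0 is set by an event that normally produces a reading. A comparator's Time 0 is a calendar date, and a reading falls on it only by chance. Difference-in-differences does not cancel an error that sits in one group and one period.

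At stake is the primary systolic estimate, and the diastolic and control outcomes that use the same readings. The share of untreated data is largest in users with few readings, and section 9.5.1 deliberately keeps them in the exposed group however little they use the system.

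**Working it through.** **Inputs from the protocol (section 11.2, sample size text).** Effect -3 mm Hg; SDs of 5 (practice), 17 (patient) and 10 (measurement); at least 4 readings per patient; 25% uptake; 8 practices of 100 patients, so 200 users and 600 non-users; 5% level, taken as two-sided. The number of after-period readings per user is not given. It is written k below and varied. Clinic readings count towards k, because section 11.2 takes readings from the health record as well as from the system.

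**Step 1. Reproduce the stated power (91%).** The model is a three-level random-intercept model with linear time, home/clinic, exposure and the exposure-by-period term. The 4 readings are assumed to fall at random over the 24 months, with home/clinic at random. The expected standard error of the interaction is 0.898. Power = Φ(3/0.898 − 1.96) = Φ(1.38) = 91.6%, which agrees with the protocol.

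**Step 2. Before/after contrast.** Let every after reading carry the true effect except the one on day 0. The user's after-period mean then shifts by

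−3 × (k − 1)/k.

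| k | Example | Estimate (mm Hg) | Loss |
|---|---|---|---|
| 2 | one upload, one later clinic reading | −1.50 | 50% |
| 4 | one upload, three later clinic readings | −2.25 | 25% |
| 13 | about monthly | −2.77 | 8% |
| 53 | about weekly | −2.94 | 2% |

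With day 0 left out, the estimate is −3.00 in every row. Generalised least squares fits that add the linear time term depend on the assumed schedule of readings. They give about −1.3 to −1.6 (k=2), −2.1 to −2.3 (k=4), −2.6 to −2.8 (k=13) and −2.9 (k=53).

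**Step 3. What this means for power, as an illustration.** Take 800 patients with 2 before and 2 after readings, day 0 being one of the users' two. The SD of a patient's change is 10 × √(1/2 + 1/2) = 10, and the standard error is 10 × √(1/200 + 1/600) = 0.816.
- Day 0 kept, expected effect −1.5: Φ(1.5/0.816 − 1.96) = 45%.
- Day 0 dropped, one after reading left in each group: the SD is 10 × √(1/2 + 1) = 12.25 and the standard error 1.00, so Φ(3/1.00 − 1.96) = 85%.

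The planned study is far larger (at least forty practices with 336 eligible patients each, or 13,440). Bias is the main issue there, and it does not shrink with sample size.

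**Step 4. If the interaction also allows a slope after Time 0.** Take k=13 at months 0 to 12 and a true step of −3. The mean is −2.77, which is the fitted value at 6 months. The spurious slope is 3 × (0 − 6)/182 = −0.099 per month, where 182 is the sum of squared deviations of the months from 6. At 12 months the estimate is −2.77 − 6 × 0.099 = −3.36, an overstatement. If the true effect instead builds linearly from zero over the year, this model is unbiased with day 0 included (k of 3 or more).

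**Step 5. Keep lag separate.** Suppose uploads are daily for a week and then monthly, with no effect until week 1 (assumed). The fitted effect is −2.19, or −2.25 with day 0 dropped. With weekly and then monthly uploads and no effect until week 4 (assumed), it is −2.53, or −2.61 with day 0 dropped. Dropping day 0 thus recovers only about 0.05 to 0.08 mm Hg of a shortfall of roughly 0.5 to 0.8. If only day 0 is untreated, both schedules give about −2.89.

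**The case against.** **Time 0 is not stated to be the first upload.** This is correct, and section 8.3 also speaks of registered users. If Time 0 were registration, however, the first reading would fall on or after it and would still count as exposed. What stands is that a rule keyed to the day after Time 0 works only once Time 0 is tied to the first reading.

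**The direction is not certain.** This stands. Shrinkage is expected under a before/after contrast, which is the natural reading of the interaction term, but Step 4 shows that a slope can reverse it at 12 months. The rule of taking the lowest value of the day may also offset part of the loss: for two independent readings with SD 10 (assumed) the minimum is on average 5.6 mm Hg lower, which matters if day 0 holds more readings than later days.

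**The size may be trivial.** For frequent uploaders it is. A reader might also infer that a user who uploads once shows no effect at all. The documents do not support this, because later clinic readings enter the analysis too.

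**Early weeks without effect belong to the question.** The outcome is defined over the first year of use, so delayed effect is part of what is being estimated. A reader might use the Step 5 shortfalls as the size of the Time 0 problem, but they measure lag.

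**It is partly handled.** Section 12.3 offers an analysis of readings closest to 6 and 12 months, but only for consideration. Section 12 restricts a secondary analysis to users with more than 3 recorded occasions, and section 11.2 has a subgroup of users for at least 6 months. None of these changes the primary analysis. Nor is this merely detail left to a later SAP: the protocol states the rule, and section 11.1 makes a formal SAP conditional.

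**Conclusion.** The point holds as a modest but avoidable misclassification. The protocol places the Time 0 day in the exposed period, and no primary-analysis rule removes the reading that normally sets that date. Under a before/after contrast the expected loss is about 1/k per user: half at two after readings, a quarter at four, 8% at thirteen and 2% at fifty-three. The study-wide loss is a weighted mix of these and cannot be fixed from the protocol, which gives no distribution of k.

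The conclusion rests on three assumptions: that Time 0 coincides with the first transmitted reading, that this reading alone is unaffected, and that the effect is a before/after step. An unqualified claim that the rule dilutes the effect would go too far, because the direction depends on the final model form.

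**What to change.** In section 11.2 (Exposures and Timeframe):
- Define Time 0 for users operationally as the date of the first transmitted reading.
- Exclude readings dated Time 0 from the after period in both groups, and begin that period the next day.
- Report users' Time 0 values descriptively as their starting home blood pressure.

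A sensitivity analysis that omits the first weeks in both groups is optional. It addresses lag, a separate issue, and should not be justified with the Time 0 figures.

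The cost is a sentence or two of text and no new data. One reading day per user is lost, and users who upload only once then contribute only clinic readings after Time 0. Comparators lose almost nothing, since they rarely have a reading on that date.

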## 12. Analytical populations

The primary analysis use data from all eligible patients. Analysts will not be blinded to the exposure status. Secondary analysis will be limited to patients in the exposed group who recorded BP measurements through the Hypertension Plus system on more than 3 occasions ("per-protocol" type analysis)

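### Section 11.2 ends the primary exposure when use stops, Sections 9.5.1 and 12.3 keep every user in the intervention group, and the primary model does not say which rule it follows

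*Protocol*

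**What the plan says.** Three places define who counts as exposed, and for how long.

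- **Section 11.2, Exposures.** The subsection opens with this definition: "The primary exposure will be use of the Hypertension Plus monitoring system, defined by SNOMED codes recorded in the clinical system compared to no use". From the start date, Time 0, "patients will be classified as exposed from this date onwards"; before it the same patients count as unexposed. Then: "Where a practice or individual stops using the system, this will be classed as the end of exposure". The unexposed group is made up of patients who never use the system.
- **Section 9.5.1.** An active user is anyone with the relevant SNOMED code. "This definition will be regardless of how much use is made of the system and once labelled as having received the intervention", the patient is analysed in that group by intention to treat.
- **Section 12.3, row 8 (withdrawal bias).** The issue named is inconsistent use of the system. The mitigation is: "We will use intention to treat approach so individuals with any Hypertension Plus activity recorded will be assigned to intervention".

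The analysis text then relies on the exposure without restating it. Section 11.2 (Statistical modelling) puts an exposure indicator and its interaction with time period in the model for systolic pressure, and adds: "The effect of the Hypertension Plus intervention at 6 and 12 months will be estimated". Section 12 (Analytical populations) says: "The primary analysis use data from all eligible patients". It also states that analysts will know the exposure status.

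**The concern.** The first rule, if used in the model, aims at the effect while the system is in use. The second aims at the effect of having started it. These are different quantities whenever some patients or practices stop within the 12 months, and the protocol attaches the first rule to the primary exposure without marking it as secondary or as a sensitivity analysis.

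Stopping happens after Time 0 and need not be random. It could follow good control, poor control or loss of interest. An analysis that drops, censors or recodes readings from that point conditions on the very behaviour that row 8 says is dealt with by intention to treat. Because the analysts are unblinded and the text supports either choice, the choice could be made after the estimates are known.

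**Working it through.** **1. The rules side by side**

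| Question | 11.2 Exposures | 9.5.1 and 12.3 row 8 |
|---|---|---|
| When does exposed status begin? | At Time 0 | With any recorded use |
| When does it end? | When the patient or practice stops | It does not end |
| What happens to later readings? | Not stated | Analysed in the intervention group |

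Under 11.2 the later readings have no category. They are no longer exposed, and the unexposed group is reserved for people who never used the system. They will nevertheless be in the data, because Section 11.2 (Timeframe of outcome measurement) extracts 12 months either side of Time 0 for all patients.

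**2. Does another section settle it?**

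- *Statistical modelling* names an exposure indicator but not its definition.
- *Section 12* keeps all eligible patients in the primary analysis but is silent on readings after stopping. Its secondary analysis is defined by more than 3 recorded occasions of use, not by a stopping date.
- *Subgroup analysis* has a group with at least 6 months of use, again not defined by a stopping date.

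No section says that the end date is ignored in the primary analysis or kept for a sensitivity analysis.

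**3. The plan's own figure**

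Inputs from the sample-size text in Section 11.2: effect -3 mm Hg; SDs of 5 (practice), 17 (patient) and 10 (measurement); at least 4 readings per patient; 25% uptake; 8 practices x 100 patients; stated power 91%. Assumed here: a two-sided 5% test, half of readings at home, and readings spread at random from month -12 to month +12.

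The generalised least squares standard error of the exposure-by-period term is 0.934. Power = Φ(|effect|/SE - 1.96) = Φ(3/0.934 - 1.96) = Φ(1.25) = 89.5%, close to the stated 91%. With a fixed two readings before and two after, it is 95.5%. The protocol does not say how the readings fall, so 91% is plausible.

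**4. Size of the gap between the rules**

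The protocol gives no stopping rate. Let s be the share of exposed patients' post-Time 0 readings that are taken after stopping. Assume that stopping is unrelated to blood pressure and that the effect ends with use.

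- Ending exposure at stopping: -3.0 for any s.
- Keeping patients in the group: -3(1 - s).
- Difference: 3s.

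| s (assumed) | Kept in group (mm Hg) | Exposure ended (mm Hg) | Gap (mm Hg) |
|---|---|---|---|
| 10% | -2.7 | -3.0 | 0.3 |
| 20% | -2.4 | -3.0 | 0.6 |
| 40% | -1.8 | -3.0 | 1.2 |

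Putting both codings through the three-level model gave -2.39 against -3.00 at s = 20%, and -1.78 against -3.00 at s = 40%, in line with the formula.

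**5. Sensitivity to carry-over**

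If a fraction c of the effect persists after stopping and the later readings are dropped under the first rule, the gap is 3s(1 - c). At s = 20% and c = 50% it is 3 x 0.20 x 0.50 = 0.3 mm Hg instead of 0.6.

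**The case against.** The best defence is that the passages speak of different things. Sections 9.5.1 and 12.3 fix the group a patient belongs to, while 11.2 merely dates the period of use. They collide only if the end date enters the primary model, and nothing says that it does. Several features favour a fixed group label:

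- If exposure were coded 0 before Time 0 and 1 after, its interaction with a before/after period would equal the exposure term itself, so the difference-in-differences interaction would be redundant.
- The workload model has only before/after, exposure and their interaction, with no state for readings after stopping.
- Outcomes are extracted over the full 12 months for all patients.

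This stands in part. A reader might infer that the protocol prescribes two complete and competing primary effects. The documents do not support that: 11.2 never finishes its rule, and the model structure leans towards intention to treat.

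It does not remove the conflict. The sentence sits in the definition of the primary exposure, next to text that already makes exposure vary over time by calling users unexposed before Time 0. An analyst applying it as written has grounds to end exposure at stopping. Even the mildest version, censoring later readings while keeping the label, departs from intention to treat. Nor can the point simply be left to an analysis plan: two stated rules conflict, and Sections 11.1 and 12.4 leave it open whether such a plan will be written.

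A reader might also take 0.6 or 1.2 mm Hg as the shift that the conflict causes. The documents give no basis for that. The stopping share is assumed, and zero carry-over is an extreme case, since Section 5 attributes improved control mainly to better management of medication, which may outlast use of the app. The formula also needs non-selective stopping, whereas the worry about bias is that stopping is selective; selection could move the gap either way.

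**Conclusion.** The inconsistency is real and concerns the primary exposure. The end-of-exposure sentence in 11.2 does not fit with 9.5.1 or row 8 of 12.3, the handling of later readings is unstated, and the model text does not say which definition it uses. The contradiction is textual and rests on no assumption.

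Bias is conditional: it arises only if the end date is used in the primary model and stopping is related to blood pressure. The size is illustrative: a gap of at most 3s mm Hg with a -3 mm Hg effect, non-selective stopping and no carry-over, and less if the effect persists.

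Power is not the issue. Keeping all users at s = 40% would need about 800 x [(1.960 + 1.282)/(1.960 + 1.341)]² / 0.6² = 2,143 patients for 90% power, calibrated to the stated 91%. At least 40 practices with 336 eligible patients each would give 13,440. What is open is which effect will be reported, and that should be settled before analysis begins.

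**What to change.** Remove the end-of-exposure sentence from the primary exposure definition in 11.2. Replace it with a statement, consistent with 9.5.1 and 12.3, that once a user code is present all of that patient's readings from Time 0 to 12 months are analysed as exposed, whether or not use continues. Say under Statistical modelling that the exposure indicator follows this definition.

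If an effect during use is also wanted, label it as a separate secondary or sensitivity analysis and state whether readings after stopping are dropped, censored or recoded. Leave the Section 12 analysis of patients with more than 3 recorded occasions as it is; it answers another question and needs no end date.

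The cost is a few sentences and no new data. The downside is that the primary estimate may be less favourable to the system than one limited to time in use.
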